10. History of recurrent bacterial cholangitis or recent episode within 3 months before Screening
11. Endoscopic interventions with therapeutic intent such as biliary duct dilation within 3 months before Screening or planned during the study
12. History of significant small bowel resection or short bowel syndrome
13. Presence of a concomitant disease or a history of any medical condition that, in the opinion of the Investigator, could pose undue risk to the subject, impede completion of the study procedures, or would compromise the validity of the study measurements
14. Clinically relevant medical history, physical examination, vital sign, standard 12-lead electrocardiogram (ECG), chemistry, hematology, urinalysis, or coagulation results at Screening beyond what is expected for subjects with a cholestatic disorder that would place the subject at undue risk as deemed by the Investigator
15. Has any of the following laboratory results at Screening:
  - a. Total bilirubin >2.0 mg/dL; total bilirubin >2.0 mg/dL is acceptable for subjects with medically documented Gilbert's syndrome if direct bilirubin is <0.3 mg/dL
  - b. Alanine aminotransferase (ALT) or aspartate aminotransferase (AST) >5× ULN
  - c. ALP >10× ULN
  - d. International normalized ratio (INR) >1.3
  - e. Platelet count <150,000/μL
  - f. Urine albumin to creatinine ratio ≥30 mg/g
16. Estimated glomerular filtration rate <60 mL/min/1.73 m^2 as determined by the Chronic Kidney Disease Epidemiology Collaboration equation at Screening
17. History of human immunodeficiency virus (HIV) or positive for HIV infection at Screening
18. Significant history of abuse of drugs, solvents, or moderate alcohol consumption (≥1 serving or unit/day on average for women and ≥2 servings or units/day on average for men; 1 unit = 12 ounces [350 mL] of 5% alcohol beer, 5 ounces [150 mL] of 12% wine, or 1.5 ounces [45 mL] of 80 proof distilled spirits) in the past 2 years before Screening
19. Has received a prohibited medication within 2 weeks or 5 half-lives of Day 1, whichever is longer, as described in [Section 8.4.1](#)
20. Participation in any clinical study with an investigational or approved drug/device within 30 days before Screening or is planning to participate in another clinical study with an investigational or approved drug/device while enrolled in this study
21. History of known or suspected hypersensitivity to any component of the study drug

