#### **12.13.3. Monitoring and Management of Potential Drug-Induced Liver Injury**

Subjects will be assessed for potential DILI during both the Double-Blind Treatment Period and Open-Label Extension Period according to the consensus guidelines for clinical trials in adults with chronic cholestatic liver disease (Palmer 2020). Monitoring, interrupting, and stopping rules based on multiples of ULN, threshold values, baseline values, and/or nadir values of ALT, AST, ALP, and total bilirubin and liver-related symptoms are described in the algorithms for treatment-emergent hepatocellular and cholestatic DILI signals presented below.

Elevated ALP values should be confirmed to be of hepatic origin with GGT. Examples of liver-related symptoms include severe fatigue, nausea, new onset of or worsening of pruritus, right upper quadrant pain, immunologic reaction (eg, rash, >5% eosinophilia), and hepatic decompensation. If the algorithm calls for repeat blood tests, the tests are to be performed within 2 to 5 calendar days after receipt of laboratory values by the site for hepatocellular DILI signals and within 7 to 10 calendar days after receipt of laboratory values by the site for cholestatic DILI signals. ALT, AST, ALP, and total bilirubin, at a minimum, will be assessed as part of the repeat blood tests.

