**Monitoring for Hepatocellular Injury**

The algorithm for monitoring and interrupting study drug for treatment-emergent hepatocellular DILI signals in subjects with a normal ALT baseline value is provided in [Table 5](#).

**Table 5: Algorithm for Monitoring and Interrupting Study Drug for Treatment-Emergent Hepatocellular DILI Signals in Subjects with a Normal ALT Baseline Value**

Treatment-Emergent ALT	Bilirubin	Liver-Related Symptoms	Action
ALT $\geq 5 \times$ ULN	Normal Gilbert's syndrome or hemolysis: No change in baseline total bilirubin	None	Repeat blood tests and monitor for symptoms.
ALT $\geq 8 \times$ ULN	Normal or elevated	None or present	Interrupt study drug and repeat blood tests. Study drug can be restarted if another etiology (not hepatocellular injury) is identified and abnormalities return to baseline levels.
ALT $\geq 3 \times$ ULN	Total bilirubin $\geq 2 \times$ baseline Gilbert's syndrome or hemolysis: direct bilirubin $> 2 \times$ baseline if baseline $> 0.5$ mg/dL	None or present	
ALT $\geq 5 \times$ ULN	Normal or elevated	Present	

ALT = alanine aminotransferase; DILI = drug induced liver injury; ULN = upper limit of normal.

The algorithm for monitoring and interrupting study drug for treatment-emergent hepatocellular DILI signals in subjects with an elevated ALT baseline value is provided in [Table 6](#).

**Table 6: Algorithm for Monitoring and Interrupting Study Drug for Treatment-Emergent Hepatocellular DILI Signals in Subjects with an Elevated ALT Baseline Value**

Treatment-Emergent ALT	Bilirubin	Liver-Related Symptoms	Action
ALT $\geq 3 \times$ baseline	Normal Gilbert's syndrome or hemolysis: No change in baseline total bilirubin	None	Repeat blood tests and monitor for symptoms.
ALT $\geq 5 \times$ baseline	Normal or elevated	None or present	Interrupt study drug and repeat blood tests. Study drug can be restarted if another etiology (not hepatocellular injury) is identified and abnormalities return to baseline levels.
ALT $\geq 2 \times$ baseline	Total bilirubin $\geq 2 \times$ baseline Gilbert's syndrome or hemolysis: direct bilirubin $> 2 \times$ baseline if baseline $> 0.5$ mg/dL	None or present	
ALT $\geq 2 \times$ baseline	Normal or elevated	Present	

ALT = alanine aminotransferase; DILI = drug induced liver injury.

Monitoring for Cholestatic Injury

The algorithm for monitoring and interrupting study drug for treatment-emergent cholestatic DILI signals is provided in [Table 7](#).

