**Table 7: Algorithm for Monitoring and Interrupting Study Drug for Treatment-Emergent Cholestatic DILI Signals**

Treatment-Emergent ALP	Bilirubin	Liver-Related Symptoms	Action
ALP $\geq 2\times$ baseline without alternative explanation	Normal Gilbert's syndrome or hemolysis: No change in baseline total bilirubin	None	Repeat blood tests and monitor for symptoms.
	Total bilirubin $\geq 2\times$ baseline Gilbert's syndrome or hemolysis: direct bilirubin $> 2\times$ baseline if baseline $> 0.5$ mg/dL	None or present	Interrupt study drug and repeat blood tests. Study drug can be restarted if another etiology (not cholestatic injury) is identified and abnormalities return to baseline levels.
	Normal or elevated	Present	
ALP $\geq 3\times$ baseline without alternative explanation	Normal or elevated	None or present	

ALP = alkaline phosphatase; DILI = drug induced liver injury.

In addition to the algorithms above, the Investigator may use clinical judgement to increase monitoring for DILI or interrupt or discontinue study drug as warranted for reasons of subject safety. An episode of DILI leading to hepatic decompensation in a study subject will result in permanent study drug discontinuation.

If a subject cannot return to the study site for a scheduled or unscheduled visit, or an immediate assessment is required, the use of a local laboratory is acceptable at the discretion of the Investigator. All local laboratory values obtained as part of DILI monitoring as well as their normal ranges are to be collected and entered into the clinical database.

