### 14. STATISTICS

Summaries will be presented for both the Double-Blind Treatment Period and the Open-Label Extension Period separately. Data summaries will use descriptive statistics (n, mean, standard deviation, median, minimum, and maximum) for continuous variables and frequency and percentage for categorical and ordinal variables. Unless otherwise specified, endpoints will use the last pre-treatment value available prior to the first dose of study drug as baseline. All data collected will be included in subject data listings.

A formal Statistical Analysis Plan (SAP) will be prepared and finalized before database lock. Additional statistical analysis details will be included in the SAP.

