#### 4.1.2 Definition of Baseline

Baseline will be defined as follows:

- For WI-NRS analysis, the average WI-NRS score using the daily values from the week before the first dose of study drug (Visit 2 [Day 1]) will serve as the baseline score. The WI-NRS value reported on Visit 2 [Day 1] is to be collected prior to the study visit according to the clinical study protocol and will be used in the baseline derivation. Day -6 through Day 1 will reflect the seven days of data reporting to be utilized.
- using the daily values from the 14 days before the first dose of study drug (including the WI-NRS score captured on the study day 1 of dosing) will serve as the baseline bi-weekly score.
- For all other study assessments, baseline is the last pre-treatment value available prior to the first dose of study drug.

Change from baseline summaries of the Open-Label Extension Period will utilize the same baseline definition derived in the Double-Blind Treatment Period. Change from the initiation of OLE will also be summarized for the Open-Label Extension Period summaries; change from the initiation of OLE will compare OLE assessments with the subject's Week 6 [Visit 6] reported assessment or last available measurement in the event Week 6 is not reported.

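### Read naturally, the direct-bilirubin stopping line for Gilbert's syndrome in Tables 5 to 7 cannot fire for the subjects exclusion 15a admits with direct bilirubin below 0.3 mg/dL

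*Protocol*

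**What the plan says.** Protocol 12.13.3 sets the rules for interrupting study drug on liver signals. In Tables 5 and 6 one interruption row pairs a moderate ALT rise with a bilirubin criterion. The cell for that criterion has two lines. The general one is "Total bilirubin $\geq 2 \times$ baseline". The one for Gilbert's syndrome or hemolysis is "Gilbert's syndrome or hemolysis: direct bilirubin $> 2 \times$ baseline if baseline $> 0.5$ mg/dL". Table 7 repeats it for ALP: "Gilbert's syndrome or hemolysis: direct bilirubin $> 2\times$ baseline if baseline $> 0.5$ mg/dL". The synopsis carries copies of all three tables.

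Protocol 8.2, criterion 15a, excludes total bilirubin above 2.0 mg/dL at Screening, with one exception: "total bilirubin >2.0 mg/dL is acceptable for subjects with medically documented Gilbert's syndrome if direct bilirubin is <0.3 mg/dL".

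Baseline is not the Screening value as such. Protocol 14 says that "endpoints will use the last pre-treatment value available prior to the first dose of study drug as baseline", and SAP 4.1.2 says the same for assessments other than WI-NRS: "baseline is the last pre-treatment value available prior to the first dose of study drug". Chemistry, including direct bilirubin, is drawn at Screening and again on Day 1.

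When a row calls for repeat tests, "ALT, AST, ALP, and total bilirubin, at a minimum, will be assessed as part of the repeat blood tests". Direct bilirubin is not named there.

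**The concern.** The condition on the Gilbert's line and the entry limit for Gilbert's subjects do not overlap. One requires a baseline above 0.5 mg/dL; the other admits subjects only below 0.3 mg/dL. The tables do not say whether the conditioning baseline is direct or total bilirubin, nor what applies at or below the floor. Direct bilirubin is the subject of the clause, so that is how most readers will take it. The line is then switched off for the very subjects whom 15a admits because of Gilbert's syndrome.

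At stake is whether a clear rise in direct bilirubin together with a moderate enzyme rise leads to interruption and an early repeat test. A second risk is that sites reading the word differently act differently on the same laboratory values.

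**Working it through.** **Inputs.** Trigger condition: baseline above 0.5 mg/dL, then direct above 2 times baseline (Tables 5 to 7). Entry limits for this group: total above 2.0, direct below 0.3 mg/dL at Screening (15a). General line: total at least 2 times baseline. Chemistry days: 1, 8, 15, 22, 43, 64, 85 (Appendix A). Write T0 and D0 for baseline total and direct bilirubin.

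**1. Can the Gilbert's line fire?**
- Condition read as direct bilirubin: at D0 of 0.1, 0.2, 0.29, 0.3, 0.4 or 0.5 it never fires, even at an on-treatment direct value of 10 mg/dL. At D0 = 0.51 it fires above 1.02. A subject below 0.3 at Screening would need a pre-dose rise of more than 0.5/0.3 = 1.67-fold to come under it.
- Condition read as total bilirubin: a baseline total near or above 2.0 always passes, and at D0 = 0.29 the line fires above 2 × 0.29 = 0.58 mg/dL.

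**2. If the general total-bilirubin line also applies.** With indirect bilirubin fixed at T0 − D0, total reaches 2 × T0 when direct reaches 2 × T0 − (T0 − D0) = T0 + D0. The fold rise is (T0 + D0)/D0 = 1 + T0/D0. If baseline values stay within the Screening limits, the direct value needed is above 2.0 mg/dL and the fold rise exceeds 1 + 2.0/0.3 = 7.67.

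| T0 | D0 | Direct needed | Fold rise |
|---|---|---|---|
| 2.1 | 0.2 | 2.3 | 11.5 |
| 3.0 | 0.2 | 3.2 | 16 |

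**3. Worked case (Table 5).** Normal baseline ALT, T0 = 2.1, D0 = 0.2, so indirect is 1.9. On treatment, direct is 2.0, indirect is unchanged and ALT is 4 times ULN. Total = 1.9 + 2.0 = 3.9, and 3.9/2.1 = 1.86. The direct line is disabled and the total line is not met. The symptom row and the repeat-test row both start at 5 times ULN. No row applies, although direct bilirubin has risen 10-fold. A Gilbert's subject with D0 = 0.6 and total at or below 2.0, also admitted by 15a, is interrupted above 2 × 0.6 = 1.2 mg/dL.

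**4. Where interruption hangs on the bilirubin line.**
- Table 5: ALT 3 to below 5 times ULN, with or without symptoms; 5 to below 8 times ULN if asymptomatic.
- Table 6: ALT 2 to below 5 times baseline, if asymptomatic.
- Table 7: ALP 2 to below 3 times baseline, if asymptomatic.

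**5. Time to the next test.** If the Table 5 row fires, tests are repeated "within 2 to 5 calendar days after receipt of laboratory values by the site for hepatocellular DILI signals". If no row fires, the next prescribed chemistry is the next scheduled visit: 7 days later up to Day 22, then 43 − 22 = 64 − 43 = 85 − 64 = 21 days nominally.

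**6. How many subjects.** The documents give no figure. Assuming 0% to 5% of the 58 randomized are of this kind, the number is 0 to 2.9, so 0 to 3.

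**The case against.** Several points on the other side stand.

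- A floor is sensible: doubling a very low direct bilirubin is a small change, and large fold rises partly reflect a small denominator.
- The worked case lies close to the line. If indirect bilirubin also rose by 0.3, to 2.2, total would be 4.2, exactly 2 times baseline, and the total line would be met if it applies.
- The 21-day interval holds only from Week 3, and the missing repeat-test row at ALT 3 to below 5 times ULN affects every subject with a normal baseline ALT.
- Worsening pruritus counts as a liver-related symptom, itch is scored daily, and sites review responses at least twice a week. In Tables 6 and 7 the symptom row then interrupts drug at 2 times baseline whatever the bilirubin. It does not help in Table 5 below 5 times ULN.
- The repeat panel is only a minimum, and restart already requires abnormalities to return to baseline.
- Section 12.13.3 refers to consensus guidelines that may explain the 0.5 floor. That source is not available here, and the protocol's own tables state no rule below the floor.

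A reader might infer that subjects with the lowest baseline direct bilirubin need the highest on-treatment value before interruption. The rules do not support this. Under the total line the value needed is T0 + D0, which at a fixed total falls as D0 falls (2.2 at T0 = 2.1, D0 = 0.1; 2.3 at D0 = 0.2). A Gilbert's subject with D0 = 1.2 is interrupted only above 2.4, and a subject without Gilbert's at total 2.0 and direct 1.0 needs direct 3.0 if indirect is unchanged. Both exceed 2.3.

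A reader might also infer that these subjects have no protection. They do. The enzyme-only and symptom rows, discontinuation at Grade 4 (8.5.1), Grade 3 or higher reporting (12.1.2), DMC review (8.5.3, 12.3), scheduled direct bilirubin (12.8) and investigator judgement (12.13.3) all remain.

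**Conclusion.** The point holds as a minor safety gap. On the natural reading, the Gilbert's line cannot work for subjects admitted under the 15a exception unless direct bilirubin passes 0.5 mg/dL before dosing, and the protocol states no direct-bilirubin rule at or below that level. Whether the total-bilirubin line covers them is unclear; the layout suggests that the Gilbert's line replaces it. If it does cover them, it responds only above 2.0 mg/dL direct when indirect bilirubin is unchanged. The main consequence is at ALT 3 to below 5 times ULN in Table 5, where neither a symptom row nor a repeat-test row applies; in the other bands it concerns asymptomatic subjects only.

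The conclusion assumes that the condition refers to direct bilirubin and that baseline values stay within the Screening limits. On the total-bilirubin reading the trigger works, and what is left is the ambiguous wording. The count of 0 to 3 rests on an assumed share and may be zero. Efficacy analyses are not affected.

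**What to change.** In Tables 5 to 7 and the three synopsis copies:

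1. State that the baseline in the Gilbert's and hemolysis line is direct bilirubin.
2. For baseline direct bilirubin at or below 0.5 mg/dL, add an absolute on-treatment limit, for example direct above 1.0 mg/dL. This joins the existing rule without a step (2 × 0.5 = 1.0) and still ignores small changes: it is 5 times baseline at 0.2 and 3.3 times at 0.3. The documents do not supply this value, so the sponsor's hepatology experts should confirm it.

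In 12.13.3 and its synopsis copy:

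3. Add direct bilirubin to the minimum repeat tests for Gilbert's and hemolysis subjects.

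It would be tempting to close the gap by applying the total-bilirubin doubling rule to all Gilbert's and hemolysis subjects. That should not be done: it would interrupt drug for purely indirect rises, which the separate direct-bilirubin line appears meant to avoid.

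The cost is a few lines in six tables, one sentence in two places, one more analyte at repeat tests, and possibly a few more interruptions in this small group. Direct bilirubin is already in the scheduled chemistry panel, and no SAP change is required.

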**Table 7: Algorithm for Monitoring and Interrupting Study Drug for Treatment-Emergent Cholestatic DILI Signals**

Treatment-Emergent ALP	Bilirubin	Liver-Related Symptoms	Action
ALP $\geq 2\times$ baseline without alternative explanation	Normal Gilbert's syndrome or hemolysis: No change in baseline total bilirubin	None	Repeat blood tests and monitor for symptoms.
	Total bilirubin $\geq 2\times$ baseline Gilbert's syndrome or hemolysis: direct bilirubin $> 2\times$ baseline if baseline $> 0.5$ mg/dL	None or present	Interrupt study drug and repeat blood tests. Study drug can be restarted if another etiology (not cholestatic injury) is identified and abnormalities return to baseline levels.
	Normal or elevated	Present	
ALP $\geq 3\times$ baseline without alternative explanation	Normal or elevated	None or present	

ALP = alkaline phosphatase; DILI = drug induced liver injury.

In addition to the algorithms above, the Investigator may use clinical judgement to increase monitoring for DILI or interrupt or discontinue study drug as warranted for reasons of subject safety. An episode of DILI leading to hepatic decompensation in a study subject will result in permanent study drug discontinuation.

If a subject cannot return to the study site for a scheduled or unscheduled visit, or an immediate assessment is required, the use of a local laboratory is acceptable at the discretion of the Investigator. All local laboratory values obtained as part of DILI monitoring as well as their normal ranges are to be collected and entered into the clinical database.

**12.13.4. Observation for Acute Kidney Injury**

[REDACTED]. Notably, no adverse changes in serum chemistry markers (eg, creatinine and BUN) were observed with daily doses of EP547 as high as 225 mg for 1 week in healthy volunteers in the Phase 1 study. [REDACTED]

In subjects with the following serum creatinine levels, adapted from the Kidney Disease: Improving Global Outcomes (KDIGO) Clinical Practice Guideline for Acute Kidney Injury

(KDIGO 2012), interruption of study drug and repeating blood tests should be considered, preferably within 3 to 7 days:

- Increase in serum creatinine by  $\geq 0.3$  mg/dL ( $\geq 26.5$   $\mu\text{mol/L}$ ) from baseline: consider interrupting study drug, repeat blood test within 3 to 7 days
- Increase in serum creatinine to  $\geq 1.5 \times$  baseline (which is known or presumed to have occurred within the prior 7 days): interrupt study drug, repeat blood test within 3 to 5 days

These KDIGO guidelines typically apply to hospital settings, where baseline values within given timeframes (ie, the preceding 48 hours to 7 days) are available. However, in interventional studies such as the current study, values this recent will not likely be available in most cases. In such instances, the Investigator can refer to the baseline value (prior to starting study drug) and evaluate the change. In cases of AKI where an etiology is identified, the reported AE term should reflect the etiology for the impairment of renal function (eg, AKI due to hypovolemia).

Additionally, all abnormal complete blood count, serum creatinine, BUN, and urine albumin to creatinine ratio values during the Double-Blind Treatment Period and Open-Label Treatment Period are to be followed as deemed clinically necessary by the Investigator.

### 13. PHARMACOKINETICS ASSESSMENT

Blood sampling for PK of EP547 will be [REDACTED]

[REDACTED] to analyze EP547 concentrations; the metabolite profile may also be analyzed from these samples.

In the event of an SAE, the Investigator should collect, if at all possible, a blood PK sample at an unscheduled visit as part of SAE follow-up.

All PK laboratory evaluations will be conducted at a bioanalytical laboratory. Details for sample collection, processing, storage, and shipment will be provided in the Laboratory Manual.

### 14. STATISTICS

Summaries will be presented for both the Double-Blind Treatment Period and the Open-Label Extension Period separately. Data summaries will use descriptive statistics (n, mean, standard deviation, median, minimum, and maximum) for continuous variables and frequency and percentage for categorical and ordinal variables. Unless otherwise specified, endpoints will use the last pre-treatment value available prior to the first dose of study drug as baseline. All data collected will be included in subject data listings.

A formal Statistical Analysis Plan (SAP) will be prepared and finalized before database lock. Additional statistical analysis details will be included in the SAP.

### 14.1. Analysis Sets

The following analysis sets will be considered:

- **Full Analysis Set:** All subjects who are randomized and take at least 1 dose of randomized study drug will be included in the Full Analysis Set (FAS). Subjects in the FAS will be analyzed according to randomized treatment assignment. If a subject is incorrectly stratified (ie, randomized according to an incorrect stratification), the subject will be analyzed under the randomized treatment for the stratum recorded in the IWRS. All efficacy and PD analyses will be based on the FAS.
- **Per Protocol Set:** The Per Protocol (PP) Set is a subset of the FAS containing subjects who meet study eligibility requirements and have no protocol deviations that might impact the assessment of efficacy measurements. Subjects will be analyzed according to randomized treatment assignment. The PP Set will be used for sensitivity analyses relating to efficacy and PD. The type of protocol deviations governing exclusion from the PP Set will be determined prior to database lock and primary analysis, and will be detailed in the SAP.
- **Safety Analysis Set:** All subjects who are randomized and take at least 1 dose of randomized study drug will be included in the Safety Analysis Set. Safety analyses will be based upon treatment actually received.
- **PK Set:** All subjects who receive at least 1 dose of EP547 and provide adequate blood samples for bioanalysis will be included in the PK Set.

